Cephalometric analysis aids in evaluating dentofacial proportions, identifying the anatomic basis of malocclusion and analysing growth and treatment-related changes. During orthodontic treatment planning, cephalometric analysis is considered an essential diagnostic method, particularly when a skeletal discrepancy exists. The introduction of Artificial Intelligence (AI) in orthodontics solved a variety of issues as it has been evidenced to be a time-saving and reliable tool to assist in developing correct diagnosis and successful treatment plans. Computerized software can automatically identify the landmarks and complete the measurements once the digital radiograph is imported using AI technology. In addition, superimposition of serial radiographs can be performed faster, and it also allows the user to obtain several analyses at a time, identify and analyse cephalometric landmarks, face analysis, tooth and mandible segmentation, bone age determination, prediction of orthognathic surgery, and temporomandibular bone segmentation. As a result, AI is increasingly being used in orthodontic treatment to improve speed, consistency, and accuracy because it is a promising tool for facilitating cephalometric tracing in routine clinical practice and analysing large databases for research purposes. Hence, it is imperative to investigate the reliability and usability of AI in cephalometric to ensure its accuracy before relying on the software for analysis.

1.0 Introduction

Cephalometric analysis can be used to analyse the facial skeleton in a two-dimensional (2D) fashion and based on specialized lateral and anteroposterior (AP) skull radiographs in certain anatomical points (Lande et al., 2022). The invention of the cephalometer was introduced by B. Holly Broadbent in 1930, and since then, various complex analytical techniques have been introduced. Cephalometry is a fundamental diagnostic tool in orthodontics. It helps the diagnosis process by determining the aetiology of a malocclusion, making the orthodontic and orthognathic treatment planning, monitoring the changes due to growth or treatment, and able to predict the orthodontic and orthognathic treatment outcomes (Koloikitha et al, 2011).

With the rapid advancement in technology, the manual tracing method is gradually being replaced by digital cephalometric analysis software. The software is being favoured as it offers various benefits, such as easy handling, allows several analyses to be performed at a time, takes up less storage space, allows superimposition of images, provides the option to manipulate the image for instance, the size and contrast of the image for better visualization of the image, reduced radiation dose, as well as the elimination of chemical and associated environmental hazards by reducing the usage of acetate tracing paper and the view box (Albarakati et al., 2012). Identifying cephalometric landmarks in lateral cephalograms can be challenging because the skull is a highly complex 3D object which in a cephalogram is projected onto a single 2D plane, leading to overlapping structures and causing the left and right outlines to not be perfectly superimposed (Lindner et al., 2015)

In the past, drawings of lateral cephalometric analysis were performed manually by orthodontists through direct measurement of cephalometric angles using a protractor on an overlay of a tracing paper secured over the radiograph. The landmarks and planes identification on the radiograph were done using pencils and rulers, with or without the aid of a view box. (Yassir, 2021). This technique is time consuming and is subject to landmark identification error, measurement error and magnification error (Zamrik et al., 2020). However, the development of computer and software technology have led to the introduction of computer-aided cephalometric analysis which bring about significant improvements in terms of speed, quality, and reliability (Coban G et al., 2022). Computerized cephalometric can automatically identify the landmarks and complete the

measurements once the digital radiograph is imported using artificial intelligence (AI) technology.

Converting from a manual cephalometric analysis technique to a computer-assisted web-based cephalometric analysis provides many advantages, however, it requires professional supervision and may result in time wasted in front of a computer screen. In addition, a systemic review revealed little scientific evidence to support the use of automatic landmark identification when compared to manual tracing due to the greater number of errors (Yassir et al., 2021). Hence, studies on reliability and usability of AI still provide insufficient evidence, and more research should be done into that specific area.

1.1 Problem Statement

Manual cephalometric tracing and analysis can be time consuming and are frequently associated with measurement and calculation errors in addition to errors occurring due to human fatigue. Computerized cephalometric analysis software was developed to overcome these problems. This can be evident especially in research that is based on cephalometric tracing where hundreds of radiographs needed to be landmarked and measured. Furthermore, some of the cephalometric analyses involve identifying various complex anatomical landmarks that are difficult to be located. Therefore, the use of digital cephalometric analysis software is widely considered to be more convenient however the accuracy and the reliability need to be tested.

1.2 Research Questions

1. Is the accuracy of AI-based cephalometric analysis program comparable to the conventional manual cephalometric tracing method?
2. Is the reliability of AI-based cephalometric analysis program better than the conventional manual cephalometric tracing method?

1.3 Research Hypothesis

1. The accuracy of AI-based cephalometric analysis is comparable to the conventional manual cephalometric tracing method.
2. The reliability of AI-based cephalometric analysis is better than the conventional manual cephalometric tracing method.

1.4 Objective

1.4.1 General Objective

To evaluate the accuracy and reliability of AI-based cephalometric analysis programs when compared to the conventional tracing and analysis method.

1.4.2 Specific Objective

1. To investigate the accuracy of AI-based cephalometric analysis programs when compared to the conventional tracing and analysis method.
2. To investigate the reliability of AI-based cephalometric analysis programs when compared to the conventional tracing and analysis method.

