2.2 Manual Tracing Vs Web-Based AI Program Cephalometric

Manual cephalometric analysis consumes valuable time due to the tedious procedures associated with it. The risks include misreading values and the measurements obtained may be susceptible to error (P Hlongwa, 2019). The reliability of the landmark identification is also questionable as it is hard to locate the tips of the caliper exactly on to the same point during every measurement to achieve consistency result (Umut Ozsoy et al,

2009). Based on the observer's experience, manual tracing can take 15-20 minutes to complete depending on the quality of the radiographs and the number of parameters assessed (Aravind K.S et al, 2022). In addition, manual tracing technique requires the printing of radiographic films and are more prone to poor quality printing and are susceptible to magnification errors (H. Alqahtani, 2020).

To overcome these problems, AI-based fully automated cephalometry was developed. Automated cephalometric analysis is one of the major applications of AI in the field of orthodontics. In recent years, various automated cephalometric software has been developed like CephX, WeDoCeph, CHEFBOT and WebCeph which utilizes artificial intelligence for automatic landmark identification instead of manual identification (Ravi K.M et al, 2022). This can significantly reduce the time and improve the efficiency of orthodontists in carrying out cephalometric analysis and diagnosis in routine clinical practice and research. Errors due to faulty identification of landmarks can result in inaccurate cephalometric interpretation which might lead to errors during orthodontic diagnosis and treatment planning.

The term AI is mostly associated with robotics which describes the development of software or machine by technology that can easily mimic human cognitive skills and perform specific activities (Sanjeev B.K, 2021). AI is now being used more frequently in orthodontics as it helps in data mining, automated diagnostics, and landmark detection of craniofacial morphometric studies. AI can identify landmarks as accurately as human examiners and it is a viable choice for a repeated recognition of numerous cephalometric landmarks. These AI-based fully automated cephalometry are gaining popularity among orthodontists because of their ability to obtain the information of patients quickly and has significantly influenced image analysis as it helps detect the anatomical landmark points consistently.

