3.4 Methodology

Ethical approval will be obtained before the commencement of the study. Forty cephalometric radiographs will be selected. Calibration will be done prior to landmark identification to ensure agreement between the examiners.

For manual tracing, 18cm x 24cm of radiographic film images of lateral cephalograms will be obtained and traced manually on a view box using transilluminated light under dark room. Each cephalograms will be secured over the view box first, and then a sheet of matte acetate tracing paper sized 22cm x 28cm are taped over the radiographic film. Three orientation marks will be placed as a reference point over the film and the tracing paper. After that, hard and tissue landmarks will be traced onto the tracing paper manually using a HB pencil. A total of 11 anatomical landmarks will be plotted on each cephalograms which are the A point (subspinale, or A), B point (B), sella (S), nasion (N), orbitale (O), porion (Po), anterior nasal spine (ANS), posterior nasal spine (PNS), gonion (Go), menton (Me) and pogonion (Pog).

Measurements of the cephalometric parameters (8 angular and 8 linear) will be taken with the help of millimetre ruler and a protractor. All measurements will be performed twice by the same investigator with intervals of 4 weeks from the first measurements. Angular measurements ($^{\circ}$) include the SNA, SNB, ANB, FMPA, MMPA, UIA, LIA, IIA. While the linear measurements (mm) include the NA, NPog, ANS-Me, SN, LFH, UFH, MxPI, MnPI.

Table 1: Definition of the relevant cephalometric points

Cephalometric points	Definition
Point A (A)	The deepest point in the concavity of the anterior maxilla between the ANS and alveolar crest
Point B (B)	The deepest point in the concavity of the anterior mandible between the alveolar crest and Pog
Sella (S)	The midpoint of sella turcica
Nasion (N)	Junction of the frontal and nasal bones at the frontonasal suture
Orbitale (O)	The most inferior point on the infra- orbital margin
Porion (Po)	The most superior point of the external auditory meatus
Anterior Nasal Spine (ANS)	The anterior limit of the nasal floor
Posterior Nasal Spine (PNS)	The posterior limit of the nasal floor
Gonion (Go)	The most posterior and inferior point on the angle of the mandible
Menton (Me)	The most inferior point on the bony chin
Pogonion (Pog)	The most anterior point on the bony chin

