For AI-based fully automated cephalometric analysis, we will be utilizing the WeDoCeph (Audax d.o.o., software version 3.2.2). WeDoCeph software is a fully automated cephalometric portal that works on the web and can be used anytime and from anywhere. WeDoCeph software complies with essential landmark tracing and measurement. To operate the analyses, firstly lateral or periapical radiographs of the patients will be uploaded into the WeDoCeph software. Then, patient profile will be created in the system and digital images of cephalograms with high quality resolution of 300DPI will be uploaded. After the x-ray was uploaded, key-in the analysis' parameters such as analysis type, patient's identifier, age and sex. Each of the cephalometric landmarks will automatically be traced by the AI digitization of

WeDoCeph. Finally, the cephalometric measurements value will be obtained for the different parameters and the tracing analysis were saved as JPEG files. Then, it will be downloaded in portable document format (pdf) and entered into the same Microsoft Office Excel spreadsheet used for manual tracing values. The same process will be applied for all 40 digital cephalograms. Then, all of the radiographs measurements will be performed once again by the same investigator with intervals of 4 weeks from the first measurements to test for the reliability.

[figure not shown]

Figure 1: Landmarks through AI-based fully automated tracing software.

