3.5 Data Analysis

The mean, standard deviation, and standard error of the difference between the repeated measurements for each method and between the two methods will be calculated. The reliability of each method will be defined using the Pearson correlation coefficient (r^2). The level of statistical significance will be set at $P < 0.05$.

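### Objective 1 and Hypothesis 1 claim AI accuracy, but with fallible manual tracing as the only comparator the design can estimate agreement only, and section 3.5 does not say how the duplicate readings enter the comparison

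*Combined protocol and SAP*

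**What the plan says.** Section 1.4.2 of the combined protocol and SAP sets the first objective: "To investigate the accuracy of AI-based cephalometric analysis programs when compared to the conventional tracing and analysis method". Section 1.3 states the matching hypothesis: "The accuracy of AI-based cephalometric analysis is comparable to the conventional manual cephalometric tracing method". Section 1.2 asks the same as a question. Manual tracing is the only comparator in section 3.4, and no consensus reading, expert panel or other independent reference is described.

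The protocol is candid about the limits of that comparator:
- Section 1.0 calls manual tracing "subject to landmark identification error, measurement error and magnification error".
- Section 1.1 says it is "frequently associated with measurement and calculation errors in addition to errors occurring due to human fatigue".
- Section 2.2 adds "The risks include misreading values and the measurements obtained may be susceptible to error", and mentions magnification error from printed films.

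Both methods are read twice. For manual tracing, section 3.4 says "All measurements will be performed twice by the same investigator with intervals of 4 weeks from the first measurements". For the AI, "all of the radiographs measurements will be performed once again by the same investigator with intervals of 4 weeks", with reliability as the stated purpose.

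Section 3.5 plans the mean, SD and standard error of "the difference between the repeated measurements for each method and between the two methods will be calculated". It does not name the reading (first, second or mean of two) that enters the between-method difference. Table 2 in section 4.0 has one mean, SD and r² per method and one P-value per parameter. That layout also leaves the choice open.

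**The concern.** Comparing the accuracy of two methods needs a third standard against which each can be judged. With two fallible methods and nothing else, their difference cannot be divided into the error of one and the error of the other. Hypothesis 2 sharpens this, because it expects the AI to be more reliable than manual tracing. The reference for accuracy is thus the method that the investigators expect to repeat less well.

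A wide spread between AI and manual values could come largely from the manual readings, while a close match would show only that the AI reproduces this manual tracing. Neither result answers whether the software is accurate, which the summary before section 1.0 says must be known before anyone relies on it. The duplicate manual readings could reduce and quantify the random part of the problem. Because section 3.5 does not say how they are used, two analysts following it could calculate different between-method comparisons.

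**Working it through.** **Inputs.** The documents give no SD for AI or manual error, and the sample-size statement in section 3.1 gives no effect size or SD from which one could be derived. There is no figure of the plan's own to reproduce on this point. The design facts used are two manual readings per film by the same investigator (section 3.4) and the planned differences (section 3.5). The rest is assumption:
- *a* is the SD of AI error, including the AI's own repeat error.
- *m* is the SD of random manual error in a single reading.
- Errors are independent of each other and between repeats.
- Each SD ranges from 0.5 to 2 (mm or degrees).

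**Spread of the AI-manual difference**
- One manual reading: variance = a² + m², and the manual share is m²/(a² + m²).
- Mean of two: variance = a² + m²/2, and the manual share is (m²/2)/(a² + m²/2).

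| a | m | SD, one reading | SD, mean of two | Manual share, one | Manual share, mean |
|---|---|---|---|---|---|
| 1 | 0.5 | √1.25 = 1.12 | √1.125 = 1.06 | 20% | 11% |
| 1 | 1 | √2 = 1.41 | √1.5 = 1.22 | 50% | 33% |
| 1 | 2 | √5 = 2.24 | √3 = 1.73 | 80% | 67% |

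At a = m = 1, 95% limits of agreement of ±1.96 × SD would be ±2.77 with one reading and ±2.40 with the mean of two, against ±1.96 for AI error alone. Over the whole assumed range the manual share runs from 6% (a = 2, m = 0.5) to 94% (a = 0.5, m = 2) with one reading, and from 3% to 89% with the mean of two.

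**Mean of the difference.** Random manual error with mean zero leaves the mean AI-manual difference unbiased. It affects only the SD, the standard error and any limits of agreement. A systematic manual error *b*, such as magnification or a fixed examiner habit, shifts the mean difference by −b. The average of two readings that both carry *b* still carries *b*.

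**Relating repeat and between-method differences.** The manual repeat difference has variance 2m², so its SD divided by √2 gives *m*. Its raw SD must not be set directly against the SD of AI minus the manual mean, because 2m² and a² + m²/2 are on different scales. At a = m = 1 the SDs are 1.41 and 1.22, so an AI exactly as noisy as the manual reader would look better. The two SDs are equal only when a² = 1.5m², that is, a = 1.22m.

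A like-for-like quantity is Var(AI − manual mean) − ¼ Var(manual repeat difference) = (a² + m²/2) − ¼(2m²) = a². Check at a = m = 1: 1.5 − 0.5 = 1.

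**The case against.** The objective names its comparator and the hypothesis is worded relatively, so *accuracy* could be read as agreement. Hypothesis 2 also allows that manual tracing may be the less reliable method, and section 3.4 plans calibration between examiners. All of this is fair, and it makes the wording change a modest one. But section 1.1 treats accuracy and reliability as separate properties to be tested, so readers would take the result as an accuracy claim. Calibration brings examiners into line with each other; it does not supply an independent standard.

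Three stronger readings are tempting, and the documents do not support them.
- A reader might infer that the plan discards the duplicate manual readings. Section 3.5 is silent on the choice, and Table 2 fits a mean of two readings as well as a single one.
- A reader might infer that the manual repeat difference is never examined. Section 3.5 plans it in the same sentence as the between-method difference. What is missing is a step that relates the two.
- A reader might infer that all manual error is counted as AI inaccuracy. No passage attributes the whole spread to the AI, and random manual error does not bias the mean difference.

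It also stands that the sizes above follow from assumed SDs and are not evidence of how large manual error will be in this study.

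**Conclusion.** The point holds in a limited form. *Accuracy*, as used in sections 1.2 to 1.4, is not estimable from this design; agreement with conventional manual tracing is. The analysis plan leaves open which manual reading is compared with the AI, and does not use the repeat differences to interpret the between-method difference.

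The size is unknown from the documents. For illustration, with equal error SDs, random manual error makes up half of the variance of the difference with one reading and a third with the mean of two. This assumes independent errors and repeats. Averaging therefore reduces the random part without removing it, and does nothing for systematic manual error. That is why the claim must be renamed whatever the analysis: no reanalysis of these readings recovers accuracy.

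**What to change.** 1. In sections 1.2 to 1.4, replace *accuracy* with agreement with conventional manual tracing, and limit the conclusion to that.
2. In section 3.5, state that for each film and parameter the first AI output is compared with the mean of the two manual readings.
3. For each parameter, report the within-examiner manual error SD (SD of the repeat difference divided by √2) beside the mean and SD of the AI-manual difference. Do not compare the raw manual-manual SD with the SD of AI minus the manual mean. Instead, subtract one quarter of the repeat-difference variance from the variance of AI minus the manual mean, and state the assumption of independent repeat errors. Say also that any manual error repeated at both readings remains in the result.

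The cost is protocol wording, a few extra table columns and a little analysis, with no new films, readings or staff. There are two downsides: the claim is narrower, and limits of agreement would refer to a two-reading mean rather than to the single manual tracing of routine practice. If the sponsor wishes to keep an accuracy claim, an independent reference such as a multi-examiner consensus would have to be defined, which would need additional readings.

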2.0 Literature Review

2.1 Orthodontics Cephalometric Analysis

Cephalometric is an interpretation of measurements of the skull made on standardized radiographs of the living head. Since the introduction of cephalometric by Broadbent and Hofrath in the 1930s, the cephalometric technique has been regarded as an important tool for orthodontists and maxillo-facial surgeons engaged in studying dental malocclusions and the underlying skeletal discrepancies (P.Hlongwa, 2019). Cephalometric analysis aids in evaluating dentofacial proportions, diagnosis of anteroposterior and vertical discrepancies, identifying the anatomic basis of malocclusion and the evaluation of the relationship between soft tissue and dental structures (Yassir et al, 2021). It is an indispensable tool for prediction of growth, treatment planning and evaluating treatment results. It is also used to predict changes that will occur for orthodontics patients after their treatment in the future. A cephalometric tracing can be prepared and analysed manually or by a computer using a web-based artificial intelligence (AI) program. Therefore, the method used for cephalometric analysis must be accurate, safe, and highly reproducible.

2.2 Manual Tracing Vs Web-Based AI Program Cephalometric

Manual cephalometric analysis consumes valuable time due to the tedious procedures associated with it. The risks include misreading values and the measurements obtained may be susceptible to error (P Hlongwa, 2019). The reliability of the landmark identification is also questionable as it is hard to locate the tips of the caliper exactly on to the same point during every measurement to achieve consistency result (Umut Ozsoy et al,

2009). Based on the observer's experience, manual tracing can take 15-20 minutes to complete depending on the quality of the radiographs and the number of parameters assessed (Aravind K.S et al, 2022). In addition, manual tracing technique requires the printing of radiographic films and are more prone to poor quality printing and are susceptible to magnification errors (H. Alqahtani, 2020).

To overcome these problems, AI-based fully automated cephalometry was developed. Automated cephalometric analysis is one of the major applications of AI in the field of orthodontics. In recent years, various automated cephalometric software has been developed like CephX, WeDoCeph, CHEFBOT and WebCeph which utilizes artificial intelligence for automatic landmark identification instead of manual identification (Ravi K.M et al, 2022). This can significantly reduce the time and improve the efficiency of orthodontists in carrying out cephalometric analysis and diagnosis in routine clinical practice and research. Errors due to faulty identification of landmarks can result in inaccurate cephalometric interpretation which might lead to errors during orthodontic diagnosis and treatment planning.

The term AI is mostly associated with robotics which describes the development of software or machine by technology that can easily mimic human cognitive skills and perform specific activities (Sanjeev B.K, 2021). AI is now being used more frequently in orthodontics as it helps in data mining, automated diagnostics, and landmark detection of craniofacial morphometric studies. AI can identify landmarks as accurately as human examiners and it is a viable choice for a repeated recognition of numerous cephalometric landmarks. These AI-based fully automated cephalometry are gaining popularity among orthodontists because of their ability to obtain the information of patients quickly and has significantly influenced image analysis as it helps detect the anatomical landmark points consistently.

WebCeph is a web-based fully automated AI driven platform that can perform nine different cephalometric analysis and two composite analyses along with interpretation. In addition, it can be used to store and maintain an archive of digital images of a patient's cephalogram, orthopantomogram and photographs. The major advantage of using this software is that multiple cephalometric analyses can be accomplished within seconds after digital cephalogram is uploaded. Apart from quick cephalometric analyses and interpretation, features like cloud-based storage of patient's records, visual treatment simulation and superimposition can make WebCeph an efficient and promising tool for routine clinical orthodontic practice. AI-based fully automated cephalometry is more

precise because once the images are detected on-screen, measurements and data processing will occur automatically.

WeDoCeph is a fully automated cephalometric online portal that can be used anytime and anywhere and the easiest way to get cephalometric stack analyse in minutes. It is an x-ray imaging software and diagnostic tool for cephalometric analysis that has features for data analysis. It is powered by AI and widely accepted AudaxCeph technology (Peter Kobal,2021). There is an incredible editing tools added in WeDoCeph which permits for converting visibility nation and move cephalometric landmarks. This AI-based fully automated cephalometry can be used by simply uploading lateral or periapical x-ray of the patient for tracing and enter the analysis' parameters such as analysis type, patient's identifier, age, and sex. Then, algorithms of AI engine will automatically trace cephalometric landmarks, planes, arch and each soft and hard tissue silhouettes which form a strong base for cephalometric analysis. Then, the orthodontist will get the results within seconds in the forms of different reports, and they can view the results, save it, print, and analyse the results. There is no monthly or yearly subscription fee needed.

